7.1.3.1 Adverse Events of Special Interest

Adverse events of special interest are required to be reported by the investigator to Genentech immediately (i.e., no more than 24 hours after learning of the event; see Section 5.4.2 for reporting instructions). Adverse events of special interest for this study are as follows:

- Cases of potential drug-induced liver injury that include an elevated ALT or AST in combination with either an elevated bilirubin or clinical jaundice, as defined by Hy's Law (see Section 5.3.5.7)
- Suspected transmission of an infectious agent by the study treatment, as defined as: Any organism, virus, or infectious particle (e.g., prion protein transmitting transmissible spongiform encephalopathy), pathogenic or non-pathogenic, is considered an infectious agent. A transmission of an infectious agent may be suspected from clinical symptoms or laboratory findings that indicate an infection in a patient exposed to a medicinal product. This term applies only when a contamination of study treatment is suspected.

- Pneumonitis
- Colitis
- Endocrinopathies: diabetes mellitus, pancreatitis, adrenal insufficiency, hyperthyroidism, and hypophysitis
- Hepatitis, including AST or ALT > 10 x ULN
- Systemic lupus erythematosus
- Neurological disorders: Guillain Barré syndrome, myasthenic syndrome or myasthenia gravis, and meningoencephalitis, facial paresis, myelitis
- Events suggestive of hypersensitivity, infusion-related reactions, cytokine release syndrome, and hemophagocytic lymphohistiocytosis,
- Pericardial disorders
- Nephritis
- Ocular toxicities (e.g., uveitis, retinitis, optic neuritis)
- Myositis
- Myopathies, including rhabdomyolysis
- Grade ≥ 2 cardiac disorders
- Vasculitis
- Autoimmune hemolytic anemia
- Severe cutaneous reactions (e.g., Stevens-Johnson syndrome, dermatitis bullous, toxic epidermal necrolysis)

7.1.4 Reporting to the FDA

The conduct of the study will comply with all FDA safety reporting requirements. **PLEASE NOTE THAT REPORTING REQUIREMENTS FOR THE FDA DIFFER FROM REPORTING REQUIREMENTS FOR HRPO/QSMC.** It is the responsibility of the Washington University Sponsor-Investigator to report to the FDA as follows:

- Report any unexpected fatal or life-threatening suspected adverse reaction (refer to Appendix B for definitions) no later than **7 calendar days** after initial receipt of the information.
- Report a suspected adverse reaction that is both serious and unexpected (SUSAR, refer to Appendix B) no later than **15 calendar days** after it is determined that the information qualifies for reporting. Report an adverse event (refer to Appendix B) as a suspected adverse reaction only if there is evidence to suggest a causal relationship between the drug and the adverse event, such as:
 - A single occurrence of an event that is uncommon and known to be strongly associated with drug exposure
 - One or more occurrences of an event that is not commonly associated with drug exposure but is otherwise uncommon in the population exposed to the drug
 - An aggregate analysis of specific events observed in a clinical trial that

indicates those events occur more frequently in the drug treatment group than in a concurrent or historical control group

- Report any findings from epidemiological studies, pooled analysis of multiple studies, or clinical studies that suggest a significant risk in humans exposed to the drug no later than **15 calendar days** after it is determined that the information qualifies for reporting.
- Report any findings from animal or in vitro testing that suggest significant risk in humans exposed to the drug no later than **15 calendar days** after it is determined that the information qualifies for reporting.
- Report any clinically important increase in the rate of a serious suspected adverse reaction of that listed in the protocol or IB within **15 calendar days** after it is determined that the information qualifies for reporting.

Submit each report as an IND safety report in a narrative format or on FDA Form 3500A or in an electronic format that FDA can process, review, and archive. Study teams must notify the Siteman Cancer Center Protocol Development team of each potentially reportable event within 1 business day after initial receipt of the information, and must bring the signed 1571 and FDA Form 3500A to the Siteman Cancer Center Protocol Development team no later than 1 business day prior to the due date for reporting to the FDA.

Each notification to FDA must bear prominent identification of its contents (“IND Safety Report”) and must be transmitted to the review division in the Center for Drug Evaluation and Research (CDER) or in the Center for Biologics Evaluation and Research (CBER) that has responsibility for review of the IND. Relevant follow-up information to an IND safety report must be submitted as soon as the information is available and must be identified as such (“Follow-up IND Safety Report”).

7.1.5 Reporting to Secondary Sites

The Washington University Sponsor-Investigator (or designee) will notify the research team at each secondary site of all unanticipated problems involving risks to participants or others that have occurred at other sites within **10 working days** of the occurrence of the event or notification of the Sponsor-Investigator (or designee) of the event. This includes events that take place both at Washington University and at other secondary sites, if applicable. Refer to Section 16.0 (Multicenter Management) for more information.

7.2 Secondary Site Reporting Requirements

The research team at each secondary site is required to promptly notify the Washington University Sponsor-Investigator and designee of all serious adverse events (refer to Appendix B, Section D) within **1 working day** of the occurrence of the event or notification of the secondary site’s PI of the event. This notification may take place via email if there is not yet enough information for a formal written report (using FDA Form 3500a

(MedWatch) and Washington University's cover sheet (Appendix D)). A formal written report must be sent to the Washington University Sponsor-Investigator and designee within **4 calendar days** (for fatal or life-threatening suspected adverse reactions) or **11 calendar days** (for serious unexpected adverse reactions) of the occurrence of the event or notification of the secondary site's PI of the event.

The research team at a secondary site is responsible for following its site's guidelines for reporting applicable events to its site's IRB according to its own institutional guidelines. The research team at Washington University is responsible for reporting all applicable events to the FDA and Genentech as needed.

Washington University pre-approval of all protocol exceptions must be obtained prior to implementing the change. Local IRB approval must be obtained as per local guidelines. Washington University IRB approval is not required for protocol exceptions occurring at secondary sites.

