| Study Population: | During stage 1 of this study, 18 patients with stage II melanoma who have undergone complete resection and who have tested positive for ctDNA will be enrolled in each arm (atezolizumab + tiragolumab (treatment) vs. atezolizumab monotherapy (reference)) for a total of 36 patients randomized. If at least 3 patients in the atezolizumab + tiragolumab arm are shown to be ctDNA negative at C3D1, stage 2 of the study will begin enrollment. Stage 2 consists of 25 patients all enrolled to the atezolizumab + tiragolumab arm (no randomization and no atezolizumab monotherapy arm). With an anticipated ctDNA positive rate of 25%, a total of approximately 144 patients will need to be consented for ctDNA testing in stage 1 and 100 in stage 2. |
| Phase: | II |
| Description of Sites / Facilities Enrolling: | This study will be open at the Siteman Cancer Center at Washington University School of Medicine as well as other cancer centers in the United States. |
| Description of Study Intervention: | 
Patients who test positive for ctDNA will be randomized on a 1:1 basis during stage 1 to either treatment with atezolizumab and tiragolumab or treatment with atezolizumab alone. If, after the completion of stage 1, it is determined that enrollment will continue in stage 2, patients will not be randomized and all will receive treatment with atezolizumab and tiragolumab.
 
Atezolizumab is given as an IV infusion at a dose of 1680 mg every 4 weeks and tiragolumab is given as an IV infusion at a dose of 840 mg every 4 weeks.
 |
| Study Duration: | Study duration is anticipated to be 84 months (24 months for accrual + 12 months for treatment + 36 months for follow-up + 12 months for data analysis). Primary analysis will take place after all patients have completed adjuvant therapy. Additionally, an interim analysis will occur after 18 patients have been accrued to the treatment arm (atezolizumab + tiragolumab). |
| Participant Duration: | Forty-eight months (12 months for treatment + 36 months for follow-up) |

SCHEMA

SCHEDULE OF ACTIVITIES

Cycles are 28 days in duration. Step 2 screening may take place up to 28 days prior to C1D1 except where noted. Safety assessments may take place +/- 3 days from time point.

| | Step 1 Screening | Step 2 Screening | D1 of each cycle | Q12W ¹ | EOT | F/U ² |
|---|------------------|------------------|--|-------------------|-----------------|------------------|
| Screening consent | X | | | | | |

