(tumor proportion score [TPS] \geq 1%) in the Phase II, global, randomized, double-blind, placebo-controlled CITYSCAPE study. As of the clinical cutoff date of Dec 2, 2019, the confirmed ORR in the intent-to-treat (ITT) population was higher in the tiragolumab combined with atezolizumab arm (37%) than in the placebo combined with atezolizumab arm (21%). Investigator assessed PFS was also improved with a stratified HR of 0.58 (95% CI: 0.38 to 0.89), with a median PFS not estimable and 3.9 months in the tiragolumab combined with atezolizumab arm compared to the placebo combined with atezolizumab arm, respectively. Responses to tiragolumab in combination with atezolizumab were observed in patients with both squamous and non-squamous histology (Rodriguez-Abreu et al, 2020).

As of the clinical cutoff date of December 2, 2019 in the CITYSCAPE study, there were 135 safety evaluable patients. The safety profile was comparable between the tiragolumab combined with atezolizumab arm and the placebo combined with atezolizumab arm in terms of all-grade adverse events (99% vs 96%), Grade \geq 3 adverse events (48% vs 44%), Grade 5 adverse events (4.5% vs 7.4%), serious adverse events (37% vs 35%), and adverse events leading to study treatment withdrawal (10.4% vs 8.8%). Study treatment related adverse events occurred at a higher frequency in the tiragolumab combined with atezolizumab arm (82%) compared to the placebo combined with atezolizumab arm (72%).

Analyzed with a comprehensive medical concepts strategy, immune-mediated adverse events were reported with a higher frequency in the tiragolumab combined with atezolizumab arm (69%) compared to the placebo combined with atezolizumab arm (47%). The difference (\geq 10% difference between arms) was predominantly attributed to events of immune mediated rash (preferred terms of rash, rash maculopapular, dermatitis, erythema, eczema, pruritic rash, folliculitis and skin ulcer) (40% vs 15%) and infusion related reactions (preferred term of infusion related reaction) (30% vs 10%).

Tiragolumab is being investigated in clinical studies as a potential therapy against various tumor types. Refer to the Tiragolumab Investigator's Brochure for details on the nonclinical and clinical studies for tiragolumab.

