7.3 Exceptions to Expedited Reporting

Events that do not require expedited reporting as described in Section 7.1 include:

- planned hospitalizations
- hospitalizations < 24 hours
- respite care
- events related to disease progression

Events that do not require expedited reporting must still be captured in the EDC.

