10.0 DATA SUBMISSION SCHEDULE

Case report forms with appropriate source documentation will be completed according to the schedule listed in this section. Data may be up to 1 cycle behind at any given time.

| Case Report Form | Submission Schedule |
|--|---|
| Original Consent Form | Prior to registration |
| On-Study Form Medical History Form Treatment Assignment Form | Prior to starting treatment |
| ctDNA Form | Baseline, C3D1, C6D1, C9D1, C12D1, end of treatment |
| Treatment Form | Every cycle |
| Toxicity Form | Continuous |
| Treatment Summary Form | Completion of treatment |
| Follow Up Form | Frequency per study calendar |
| Imaging Form | Baseline, every 12 weeks for the first 2 years after surgery, every 24 weeks for the third year after surgery |
| Recurrence Form | Time of disease recurrence |
| Death Form | Time of death |
| MedWatch Form | See Section 7.0 for reporting requirements |

Any queries generated by Washington University must be responded to within 28 days of receipt by the participating site. The Washington University research team will conduct a regular review of data status at all secondary sites, with appropriate corrective action to be requested as needed.

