14.7.1 Safety Early Stopping Rule

Early stopping of this trial is calculated based upon the report of study treatment (i.e., the combination of atezolizumab and tiragolumab, or atezolizumab monotherapy) related grade 3 or greater adverse events (AEs) (i.e., toxicities). A Bayesian safety-monitoring plan (Thall PF, Simon RM, Estey EH., 1996)²¹ will be implemented once the first 12 evaluable patients are available. A Bayesian sequential safety monitoring will be defined as $\Pr(\theta_T > \theta_0 \mid \text{data}) > 0.80$, where θ_T denotes the proportion of toxicity and θ_0 ($\theta_0=20\%$) represents the rate under null hypothesis (maximum probability of toxicity allowed). Enrollment will be stopped early whenever there is >80% chance that the event rate is larger than the null. The trial will be recommended to stop for excessive toxicities according to the toxicity stopping boundaries listed in the table below:

| Stop for excessive toxicities (grade 3 or greater) if: | |
|--|---|
| # patients who experience toxicity is \geq : | In first # patients being determined ctDNA positive |
| 4 | 12 |
| 7 | 24 |
| 10 | 36 |
| 12 | 48 |
| 15 | 61 |

The above stopping boundaries were obtained using Bayesian Toxicity Monitoring online application version 2.2.1.0 (available at <http://ibl.mdanderson.org/BTM/>) developed by M.D. Anderson Cancer Center. We assume that the parameter θ_0 is a constant and that θ_T follows a non-

informative prior of beta (0.5, 0.5). Accrual will be stopped and the event will be reviewed by the Data Safety and Monitoring Board if a study treatment-related death is observed.

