| Event | WU (Coordinating Center) | Local IRB | FDA | Genentech |
|--|---|------------------|------------|------------------|
| Adverse event or SAE that does not require expedited reporting | As per routine data entry expectations | | | |
| Protocol exception | Approval must be obtained prior to implementing the change. | | | |

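### Secondary sites must expedite only serious events, but the toxicity stopping rule counts every treatment-related grade 3+ event, so a crossing can be recognised up to 28 days late

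*Combined protocol and SAP*

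**What the plan says.** **The rule.** Section 14.7.1 counts patients with a grade 3 or higher adverse event related to study treatment in either arm. It sets no seriousness condition. The action is immediate: "Enrollment will be stopped early whenever there is >80% chance that the event rate is larger than the null".

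**The fast route from secondary sites.** Section 7.2 requires each site to "promptly notify the Washington University Sponsor-Investigator and designee of all serious adverse events (refer to Appendix B, Section D") within 1 working day. The Appendix C secondary-site table adds deadlines of 4 or 11 calendar days for suspected adverse reactions that are unexpected and serious, fatal or life-threatening, and 4 calendar days for unanticipated problems.

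**The route for everything else.** The same table handles adverse events that need no expedited report "As per routine data entry expectations". Section 7.3 says "Events that do not require expedited reporting must still be captured in the EDC".

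**Timing of data entry.** The Section 10.0 schedule has the row "Toxicity Form | Continuous", but the section opens with a general allowance: "Data may be up to 1 cycle behind at any given time". The Schedule of Activities fixes the unit: "Cycles are 28 days in duration".

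**Oversight.** Section 12.0 has the principal investigator and coordinator watch for serious toxicities on an ongoing basis. The DSMB must meet at least every six months.

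**The concern.** The rule and the reporting duty use different criteria. The rule selects events by grade and relatedness; the duty selects them by seriousness. A related grade 3 laboratory abnormality or rash managed without admission adds one to the count in Section 14.7.1, yet need not be serious under Appendix B.

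Sites that follow the protocol exactly can therefore leave the central count one short when a boundary has in fact been met. The error runs in one direction only: late entries can hide toxicity from the rule but cannot create it. This is the protocol's only quantitative toxicity stop, and it protects resected patients receiving adjuvant treatment.

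**Working it through.** **1. Reproduce the boundaries.** Inputs from Section 14.7.1: prior Beta(0.5, 0.5), limit 20%, cut-off 0.80. With r toxic patients among n, the posterior is Beta(0.5 + r, 0.5 + n − r). The boundary is the smallest r with P(rate > 0.20 | r, n) > 0.80.

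| n | Stated boundary | Posterior at boundary | Posterior with one event fewer |
|---|---|---|---|
| 12 | 4 | 0.874 | 0.688 |
| 24 | 7 | 0.868 | 0.740 |
| 36 | 10 | 0.876 | 0.779 |
| 48 | 12 | 0.809 | 0.703 |
| 61 | 15 | 0.817 | 0.725 |

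All five stated boundaries reproduce. In every row, removing one event takes the posterior below 0.80, so one unentered event is enough to keep the rule silent.

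**2. Bound the delay.** Suppose the r-th toxicity among the first n patients occurs on day T, and each entry arrives 0 to 28 days after its event. All r entries are then in by day T + 28. If a late entry updates the row it belongs to, recognition is at most 28 days late.

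**3. Convert to patients.** Planned accrual is 61 treated patients (Section 14.5) over 24 months (Protocol Summary): 61/24 = 2.54 per month. Over 28 days this is 2.54 × 28/30.44 = 2.3 patients.

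**4. Illustrate the sensitivity at 12 patients.** The true toxicity rates below are assumed. If one event is unentered, 5 true events are needed to show 4.

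| True rate | P(at least 4 of 12) | P(at least 5 of 12) | P(exactly 4 of 12) |
|---|---|---|---|
| 20% | 0.205 | 0.073 | 0.133 |
| 30% | 0.507 | 0.276 | 0.231 |
| 40% | 0.775 | 0.562 | 0.213 |

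The last column is the chance that the 12-patient row sits exactly on its boundary, where a single missing entry decides. It is not the chance that an entry is missing.

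**5. Is the non-serious share plausibly above zero?** Section 1.7 reports, for the combination in lung cancer, grade 3+ events in 48% of patients and serious events in 37%. At least 48 − 37 = 11 percentage points had a grade 3+ event and no serious event, that is 11/48 = 23% of those with a grade 3+ event. These are all-cause events in another disease, so the figure is indicative only.

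**6. Which events lack a short route?** Grade 3 hypothyroidism is not on the AESI list in Section 7.1.3.1, and its row in Section 6.3.4 has no contact step. Isolated grade 3 amylase or lipase elevation (Section 6.3.10) calls for contacting the PI only if it fails to resolve or recurs. Grade 3 rash (Section 6.3.11) does so only on non-resolution, and the AESI list covers only severe cutaneous reactions.

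**The case against.** The strongest reply is that several routes already narrow the gap, and most of it stands.

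- The Toxicity Form is scheduled as continuous, unlike the per-cycle Treatment Form. One cycle is the outer tolerance, not the schedule. Section 10.0 also promises regular review of site data status, and Section 15.0 a regular conference call.
- AESIs must reach Genentech within 24 hours whether or not serious (Sections 7.1.3 and 7.1.3.1). Section 7.2 makes the coordinating centre responsible for those reports, so it must hear of them quickly, although no site-to-centre step is written. The list covers much of the expected immune toxicity.
- Several grade 3–4 rows in Section 6.3 require contact with the PI or Medical Monitor, and Appendix B lets an important medical event count as serious without admission.
- Section 4.6 adds the first sub-site at the 6-month milestone, so the earliest patients may come mainly from the lead site.

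A reader might therefore be tempted to infer that the rule's input has no timely route at all. The documents do not support that. The gap is confined mainly to non-serious events that are not AESIs and carry no contact step.

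A reader might also infer that one missing event at a look defers the stop to the next row, 12 or 13 patients later. That treats each row as a one-time snapshot. The table counts toxicities among the first so many patients, so a late entry for one of the first 12 still completes 4 of 12 when it arrives. The instruction to stop whenever the criterion is met points the same way.

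What the reply does not remove is the written allowance. Nothing states that continuous entry overrides the one-cycle tolerance, and the remaining events have no short deadline.

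**Conclusion.** The mismatch is real and modest. Following the protocol as written, recognition of a boundary crossing can be delayed by up to 28 days, about 2 patients at planned accrual. For illustration, a simulation assumed a 30% true toxicity rate, half of patients at secondary sites, mean onset of 3 months and the full 28-day lag. When any delay occurred it averaged about 21 days, again roughly 2 patients.

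The 28-day bound assumes that sites stay within the allowance and that late entries update the row they belong to. How often a delay would occur depends on the secondary-site share, the non-serious share and the time to onset. The documents give none of these for this trial, so no frequency is claimed. No boundary or other stated figure is wrong. This is a cheap improvement to how the safety rule is executed, not a flaw that invalidates it.

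**What to change.** 1. In Section 7.2, extend the 1-working-day notice to any grade 3 or higher adverse event judged possibly, probably or definitely related to study treatment, whether or not it is serious.
2. Add a matching row to the secondary-site table in Appendix C.
3. In Section 10.0, state that grade 3+ entries on the Toxicity Form are exempt from the one-cycle allowance.

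The cost is protocol wording and one short e-mail per event. At the plan's 20% limit that is 0.20 × 61 = 12.2, or about 12 patients trial-wide, and fewer at secondary sites. The stopping boundaries stay as they are.

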7.3 Exceptions to Expedited Reporting

Events that do not require expedited reporting as described in Section 7.1 include:

- planned hospitalizations
- hospitalizations < 24 hours
- respite care
- events related to disease progression

Events that do not require expedited reporting must still be captured in the EDC.

